- If several doses are missed due to inability to tolerate oral administration (e.g. mucositis or nausea/vomiting), therapy should resume as soon as the patient is able to tolerate oral administration. Please ensure all missed doses are documented in the patient medical record if the patient is in the hospital or patient diary (*available on the COG protocol web page*) if the patient is being treated at home.

Most patients will receive the *LPB* or placebo in both the inpatient and outpatient settings. Adherence to the prescribed regimen will be measured by examination of medication administration records and as documented in the electronic medical record or other hospital source documentation. Patients will be given a diary to document the doses they take at home, which includes instructions for preparation and storage.

Adherence will be defined as administration of at least 80% of the prescribed doses. In the home setting, medication will be dispensed for a specified time period and medication diaries will be completed by families and delivered to the institution on a weekly basis at the time of weekly visits.

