9.3 Data Analytic Plan

Preliminary Descriptive Analysis: Study variables will be summarized using simple descriptive statistics such as count/percentage for categorical variables and mean/standard deviation/median/interquartile range for continuous variables. Baseline patient demographics and clinical characteristics will be summarized. The two arms will be balanced on the factors included in the stratified randomization. Treatment arms will be descriptively compared for other potential confounders for possible inclusion in the multivariate models. Arm comparison will be performed using simple two-sample tests, such as χ^2 test of proportions for categorical variables and independent t-tests or Wilcoxon rank sum tests for continuous variables. Analyses for each of the aims is presented below:

Primary Aim: The primary aim is to determine whether oral *LBP* prevents the development of Stage 1-4 GI aGvHD incidence in children and adolescents undergoing alloHCT. We hypothesize that administration of oral *LBP* will reduce the incidence of Stage 1-4 GI aGvHD compared to placebo. As described above, accrual will be conducted in two stages, the screening stage and the confirmatory stage. The proportion of 120 centrally reviewed, eligible and evaluable randomized patients who received at least 1 dose of treatment having Stage 1-4 GI aGvHD incidence from Day 0 through Day 120 will be compared between the two arms after the screening stage via two-sample unpooled chi-square test of proportions at 1-sided $\alpha=0.3$. If this liberal estimate of efficacy of *LBP* is demonstrated, accrual of the confirmatory stage will continue.

At the end of the confirmatory stage, the proportion of eligible patients having Stage 1-4 GI aGvHD incidence from Day 0 through Day 120 will be compared between the two arms (including patients randomized in both stages) via two-sample unpooled chi-square test of proportions at $\alpha=0.05$ (1-sided). We will use a modified intention-to-treat approach for the primary analysis.

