Secondary analyses will be performed on cumulative incidence of Stage 1-4 GI aGvHD using unconditional multivariate logistic regression with covariate adjustment. Covariates, to be considered in the statistical models are: use of total body irradiation, duration of broad spectrum antibiotic usage, incidence of *C. difficile* infection, Haplo designation, and duration of total parenteral nutrition. We expect few patients to be terminated from aGvHD observation prior to Day 120 due to death, loss to follow-up, or consent withdrawal before determination of GI aGvHD outcome. Nevertheless, we will also perform secondary analyses (*time from graft infusion to first Stage 1-4 GI aGvHD onset*) via competing risk modeling, where graft failure, relapse and death are treated as competing events, generating incident curves and comparing treatment arms with the Gray's test to accommodate censoring. Patients without Stage 1-4 GI aGvHD will be censored when they meet criteria to be off study. Actuarial analyses will be extended for covariate adjustment using Cox proportional hazards regression. If we observe moderate protocol non-compliance with the daily *LBP*, additional analyses, such as as-treated analyses, subset analyses including only patients adherent with protocol treatment, or sensitivity analyses, will be performed to assess whether treatment adherence influenced the primary outcome. Based on our pilot results, we not anticipate a significant adherence problem.

Exploratory Aim 1: This aim is to determine whether administration of *LBP* prevents the development of moderate to severe (Grade II–IV) overall aGvHD. We hypothesize that

administration of *LBP* will reduce the incidence of Grade II–IV aGvHD in alloHCT recipients compared to placebo. We will use a similar analysis approached as described above for the primary aim but using the dichotomous cumulative incidence of Grade II–IV aGvHD as the endpoint measure.

Exploratory Aim 2: This exploratory aim is to determine whether *LBP* administration maintains intestinal integrity as measured by serum citrulline levels and reduces the incidence of mucosal barrier bloodstream infections (MBIs). We hypothesize that administration of *LBP* will maintain serum citrulline levels in alloHCT patients compared to patients receiving placebo. As well, we expect a lower incidence of MBIs in the *LBP* arm compared to placebo.

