The citrulline levels at each of the time points will be summarized and described by arm. The mean quantitative change in citrulline level from start of conditioning to each of the four later time points will be compared between the 2 arms to determine if *LBP* administration maintains citrulline level via two-sample t-test and repeated-measures general linear modeling which include adjustments for potential confounders. In such analyses, multiple comparison adjustments for the 4 parallel analyses (linear contrasts) will be performed with Bonferroni adjustment to maintain an overall fixed α level. Linear mixed models, which include data from all time points for longitudinal data analyses with adjustment for within-patient correlation, will also be considered.

Likewise, we will compare the incidence of MBIs between two groups looking at the time from start of protocol treatment to first infection as the primary endpoint. Patients without infection will be censored when they meet criteria to be off study. Cox proportional hazards regression will be used to compare the incidence density of infection for the two groups adjusted for confounders (use of total body irradiation, duration of broad spectrum antibiotic usage, incidence of *C. difficile* infection, and duration of total parenteral nutrition). Main analyses for this aim will be based on a modified intention-to-treat principle (inevaluable patients will be excluded), but additional as-treated analysis, subset analysis, or sensitivity analysis may be performed if we observe issues with adherence to the randomized treatment on the study.

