APPENDIX III: ACUTE GVHD STAGING AND GRADING

Reporting Requirements for Acute GVHD in COG Studies

In an attempt to standardize reporting of acute GVHD, the COG Stem Cell Transplantation Committee has adopted a modification of guidelines that were originally developed at the University of Michigan.

Table 1 outlines standard criteria for GVHD organ staging. However, confounding clinical syndromes (such as non-GVHD causes of hyperbilirubinemia) may make staging GVHD in a given organ difficult. In addition, timing of organ specific symptoms affects whether that symptom is more or less likely to be true GVHD. Please refer to **Tables 2 and 3** to assist you in deciding whether to attribute these clinical findings to GVHD, especially in situations where a biopsy is not possible. For additional help, please see the text which follows the tables. **Table 4** reviews the approach to assessing GVHD as acute, chronic, or the overlap between the two.

Finally, *engraftment syndrome* will be reported separately from the GVHD scoring presented below.

Engraftment Syndrome

A clinical syndrome of fever, rash, respiratory distress, and diarrhea has been described, just prior to engraftment in patients undergoing unrelated cord blood and mismatched transplantation. If, in the judgment of the local investigator, a patient experiences this syndrome, details of the event should be reported when requested in the study CRFs.

Modified Glucksberg Staging Criteria for Acute Graft versus Host Disease

Table 1 Organ Staging (See tables and text below for details)

Stage	Skin	Liver (bilirubin)	Gut (stool output/day)
0	No GVHD rash	< 2 mg/dL	Adult: < 500 mL/day Child: < 10 mL/kg/day
1	Maculopapular rash < 25% BSA	2-3 mg/dL	Adult: 500–999 mL/day Child: 10 -19.9 mL/kg/day Or persistent nausea, vomiting, or anorexia, with a positive upper GI biopsy.
2	Maculopapular rash 25 – 50% BSA	3.1-6 mg/dL	Adult: 1000-1500 mL/day Child: 20 – 30 mL/kg/day
3	Maculopapular rash > 50% BSA	6.1-15 mg/dL	Adult: > 1500 mL/day Child: > 30 mL/kg/day
4	Generalized erythroderma plus bullous formation and desquamation > 5% BSA	>15 mg/dL	Severe abdominal pain with or without ileus, or grossly bloody stool (regardless of stool volume).

For GI staging: The “adult” stool output values should be used for patients > 50 kg in weight. Use 3 day averages for GI staging based on stool output. If stool and urine are mixed, stool output is presumed to be 50% of total stool/urine mix (see Section 3.2).

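### An as-treated analysis, or an adherence rule applied to the LBP arm alone, can show a benefit when LBP does nothing, because GI events can themselves interrupt dosing

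*Combined protocol and SAP*

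**What the plan says.** For the primary aim, Section 9.3 states: "We will use a modified intention-to-treat approach for the primary analysis". If moderate non-compliance with daily LBP is seen, it adds as-treated analyses, "subset analyses including only patients adherent with protocol treatment", or sensitivity analyses. Their purpose is "to assess whether treatment adherence influenced the primary outcome". Exploratory Aim 2 carries a similar provision: "additional as-treated analysis, subset analysis, or sensitivity analysis may be performed".

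Section 4.2.2 gives the threshold: "Adherence will be defined as administration of at least 80% of the prescribed doses". It also deals with runs of missed doses: "If several doses are missed due to inability to tolerate oral administration (e.g. mucositis or nausea/vomiting". Section 4.1 puts dosing at about 64 days, from the start of conditioning to Day 56. Section 9.2 counts Stage 1-4 GI aGvHD from Day 0 to Day 120. It also counts evaluable patients as having the event if they die, withdraw or are lost before their outcome is determined.

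The plan does not define the as-treated groups, quantify moderate non-compliance, say whether the adherence rule applies to both arms, or say how doses missed after GI aGvHD onset are handled.

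**The concern.** Adherence is measured over a window in which the outcome can already have occurred. A child with gut GvHD in the first weeks may be unable to take the product, and a child who dies or withdraws early both stops dosing and is counted as an event. Events would then be over-represented among the non-adherent. An analysis that takes these patients out of the LBP group, without doing the same to placebo, lowers the LBP event rate whether or not LBP works.

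The stated purpose is to learn whether adherence influenced the outcome. Where the outcome also influences adherence, a naive comparison cannot separate the two. At stake is how a supportive result would be read: a strong as-treated finding beside a weak randomized comparison could be taken as evidence that LBP works when taken properly.

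**Working it through.** **Inputs from the documents.** Event rates of 30% (placebo) and 18% (LBP), so a design difference of 12 points; 227 per arm (Section 9.4). Unpooled two-proportion test at one-sided 0.05 (Section 9.3). Adherence threshold of 80% (Section 4.2.2) of about 64 doses (Section 4.1): 20% of 64 is 12.8, so 13 missed doses make a patient non-adherent.

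**Check of the set-up.** Simulating both stages with this test (60 per arm at one-sided 0.30, then 227 per arm at one-sided 0.05; 30% v 18%; 400,000 runs) gives 80.0% overall power, matching the 80% in Section 9.4. The plan gives no figure for the adherence analyses.

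**Assumptions.** LBP has no effect, so the event rate is e = 0.30 in both arms. Non-adherence is b = 0.10 without an event and a = 0.20 to 0.50 with one. The documents do not report adherence by event status.

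**As-treated, one possible reading: adherent LBP v all other patients** (whole placebo arm plus non-adherent LBP patients).

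- Adherent LBP: e(1−a) / [e(1−a) + (1−e)(1−b)]
- All others: (e + ea) / [1 + ea + (1−e)b]

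| a | Adherent LBP | All others | Difference (points) | Apparent relative reduction | False positives |
|---|---|---|---|---|---|
| 20% | 0.24/0.87 = 27.6% | 0.36/1.13 = 31.9% | 4.3 | 13% | 26% |
| 30% | 0.21/0.84 = 25.0% | 0.39/1.16 = 33.6% | 8.6 | 26% | 64% |
| 40% | 0.18/0.81 = 22.2% | 0.42/1.19 = 35.3% | 13.1 | 37% | 92% |
| 50% | 0.15/0.78 = 19.2% | 0.45/1.22 = 36.9% | 17.7 | 48% | 99% |

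False-positive rates come from 100,000 simulated trials with 227 per arm. If a = b = 10%, both groups have 30% events and the rate is about 5%.

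**Adherence rule on the LBP arm only: adherent LBP v whole placebo arm.** Placebo stays at 30%, so the false differences across the same rows are 2.4, 5.0, 7.8 and 10.8 points, with false-positive rates of 14, 31, 56 and 81%.

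**Adherent patients of both arms, equal interruption.** The adherent-LBP formula applies to each arm. At a = 40% the rates are 22.2% v 22.2%. False positives stay at about 5% in every such scenario.

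**Adherent patients of both arms, unequal interruption.** With a = 45% in LBP and 35% in placebo, the rates are 0.165/0.795 = 20.8% v 0.195/0.825 = 23.6%, with 17% false positives. With 60% v 40%, they are 0.12/0.75 = 16.0% v 22.2%, with 44%. Exchanging the arms reverses the sign.

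**Complier-average effect** = randomized difference / share of the LBP arm that is adherent.

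- No effect, a = 40%: 0/0.81 = 0.
- True 30% v 18%, a = 40%: adherent share = 0.18 × 0.60 + 0.82 × 0.90 = 0.846, giving 12/0.846 = 14.2 points.

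**The case against.** The strongest objection concerns the adherent-only subset. A reader might infer that it too must favour LBP. Read plainly, it takes adherent patients from both arms of a double-blind trial. If LBP does nothing, the same symptoms interrupt LBP and placebo alike and the selection cancels. This stands. The subset misleads only if LBP changes who stays adherent, for example through tolerability or the rule in Section 4.2.3 that stops the product after an LBP-positive blood culture. The direction is then not fixed. Nor does selection always inflate a real effect: with 30% v 18% true rates and the 40%/10% assumption in both arms, adherent patients show 22.2% v 0.108/0.846 = 12.8%, a difference of 9.5 points rather than 12.

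Other objections stand in part:

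- The contrast of adherent LBP with all others is not written in the plan. However, no other definition is given, and the trigger speaks of compliance with LBP rather than with study product, which leaves a one-arm rule open.
- The link between events and missed doses may be weak. Onset after about Day 44 leaves too few doses to cause 13 misses. Tube dosing is allowed, and dosing resumes once tolerated. Appendix III lists "persistent nausea, vomiting, or anorexia, with a positive upper GI biopsy" under gut stage 1, but Section 9.2 says that lower GI GvHD alone is an event, which may reduce the symptom overlap. The 20% row reflects a weak link and still gives about 4 points.
- Section 9.3 expects no significant adherence problem, citing the pilot. The pilot's 97% (30/31, Section 2.5) uses a 50% dose threshold. The share below 80% is not reported.
- For Aim 2 the endpoints are citrulline and bloodstream infection, and nothing here sizes the effect on them.

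**Conclusion.** The point holds for the conditional as-treated analysis and for any adherence rule applied to the LBP arm only. With no LBP effect, the as-treated reading examined here shows a false benefit of about 4 to 18 points against a design difference of 12. This rests on a 30% event rate, on assumed non-adherence of 10% without and 20-50% with an event, and on one reading of an undefined term. If adherence is unrelated to events, the bias disappears.

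Two stronger inferences are not supported. The adherent-only comparison across both blinded arms is not biased under the null when interruption is equal. The trial's main result is not at risk either: the primary analysis is modified intention-to-treat, and the adherence analyses enter neither the screening decision nor the final test. This is an inexpensive improvement to supportive analyses, not a flaw in the design.

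**What to change.** In Section 9.3, under the primary aim:

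1. Replace the as-treated analysis with a complier-average effect using randomized arm as the instrument and the existing 80% definition, reported as a sensitivity analysis. State that it is centred on zero if LBP does nothing. State also that it can overstate a real effect (14.2 v 12 points in the example above), because the 80% cut treats partial dosing, and dosing cut short after the event, as no treatment.
2. Apply any adherent-only subset to both arms, with adherence measured only up to a landmark such as Day 14, among patients event-free at that day. Deaths and withdrawals before the landmark count as events for this purpose. State that shared causes of early missed doses and later events may remain.

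No new data are needed: Section 7.2 collects product days for each reporting period, including Day 14, and Section 9.2 collects onset dates. The cost is SAP wording and one extra model. The downsides are wider intervals than a naive subset would give, and a landmark analysis that drops patients with earlier events.

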7.1 Required Clinical and Laboratory Evaluations

Studies	Eligibility [§]	First day of conditioning ^{@.&}	Day 0 (Graft Infusion)	Day 7	Day 14	Day 28 or Discharge [%]	Day 56	Day 120
History	X	----	----	----	----	----	----	----
Physical examination, evaluation of GvHD	X	X	X	X	X	X	X	X
Performance status	X	----	----	----	----	----	----	----
Pregnancy test*	X	----	----	----	----	----	----	----
Screening for Clostridium difficile (only if diarrhea at enrollment or first day of conditioning)	X	X ^{&}	----	----	----	----	----	----
Review of LBP administration/patient diary	----	----	X	X	X	X	X	
Blood sample for citrulline and cytokine studies See Section 7.4.1	----	X [^]	X	X	X	X	X ^{a,b}	
Stool sample for correlative studies See Section 7.4.2	----	X [^]	X	X	X	X	X ^b	X ^b

§ All clinical and laboratory studies to determine eligibility must be performed within 7 days prior to enrollment/randomization unless otherwise indicated.

^ Specimen collection on first day of conditioning or anytime within 72 hours before the start of conditioning (prior to chemotherapy). See [Section 7.4.1](#) and [Section 7.4.2](#) for overview of procedures and a Specimen Collection Manual available on the COG protocol web page with further technical detail.

@ The first day of the transplant conditioning regimen is defined as the first day of chemotherapy or TBI, excluding any preceding anti T-lymphocyte antibody therapy. See [Section 4.2.1](#).

% Day 28 or day of discharge, whichever comes first.

* Women of childbearing potential, defined as a female who has had her first menstrual cycle.

& If the patient has diarrhea on the first day of conditioning and repeat stool culture shows *C. diff*, then the patient is ineligible and must be removed from protocol therapy. Reminder: patient condition(s) prior to initiation of protocol therapy must be within parameters required for eligibility. (See [Section 8.1](#))

a Citrulline sample only.

b Blood and stool specimens may be collected within 14 days of the designated time point without being considered a protocol deviation.

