7.3 Correlative Studies

7.3.1 Serum citrulline levels

Serum specimens will be evaluated for citrulline levels by the laboratory of [name] at CUMC. Serum citrulline will be evaluated from the initiation of therapy to Day 56. Given previous experience, it is predicted that serum citrulline levels are expected to nadir at Day 7 and not begin to rebound until Day 21 in patients receiving placebo. In comparison, it is predicted that patients receiving *LBP* will have a less profound decrease in mean serum citrulline at Day 7 and earlier kinetic rebound in mean serum levels, reflecting less mucosal insult as hypothesized. Given the proposed effect in maintaining and/or attenuating injury to intestinal luminal integrity, it is hypothesized that maintaining higher serum citrulline levels in patients receiving *LBP* will be associated with less GI aGvHD and less mucosal barrier insult blood stream infections (MBI BSI).

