We will randomly select a subset of 30 samples from patients with similar overall 16S abundance, but 15 samples will have abundant *LBP* and 15 additional samples will have undetectable *LBP*. We will utilize the Illumina HiSeq2000 platform, aiming for a mean of 10 gigabases of 101 bp paired-end reads per sample. For comparative quantification of gene content at the individual gene level and the level of KEGG metabolic pathways, we will utilize linear discriminate analysis (LDA) effect size (LEfSe) analysis⁸⁹ for biomarker discovery. In addition to comparing samples with abundant and reduced *LBP* levels, we will also examine samples from patients who did or did not develop aGvHD. With this approach, we hope to identify novel bacterial genes and gene pathways, some of which may be *LBP*-derived, that are associated with modulation of aGvHD and may play a role in aggravating or attenuating inflammation. As all correlative assays will be performed on the backbone of a COG clinical trial, we anticipate high quality and very complete assessment laboratory findings.

7.3.3.2 **Evaluating the effects of LBP introduction on intestinal flora function via functional metabolite profiling**

While whole shotgun metagenomic sequencing provides information regarding the functional potential of the intestinal flora, a complementary approach is to assay directly for demonstration of substrate utilization and metabolite production. By determining bacterial metabolite abundances, one can confirm that increased abundance of individual genes and genes of metabolic pathways are associated with a corresponding increase in enzymatic activity. This method can also identify novel bacterial metabolites that are biologically active. One example of a group of metabolites that have garnered interest recently is short-chain fatty acids (SCFA), which are produced by many bacteria as a byproduct of carbohydrate fermentation. SCFA have been found to be important modulators of the immune system. In germ-free mice and vancomycin-

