treated conventional mice, administration of SCFA (acetate, propionate, or butyrate) restored normal numbers of Tregs in the large intestine.⁸⁴ GPR43 (a SCFA receptor) has been identified as necessary for mediating the anti-inflammatory effects of commensal bacteria⁹⁶ and is required for restoration of large intestinal Tregs by SCFA.⁸⁴ We will quantitatively profile levels of enzymatic substrates and metabolites via UHPLC-MS services coupled with an extensive library with >2800 authenticated compounds provided by Metabolon (Durham, NC). We will profile aliquots of the same stool samples selected for the whole shotgun metagenomic sequencing approach detailed above as well as paired serum samples collected at the same time as the stool samples. A recent study linking intestinal flora with severity of an autism-like syndrome in mouse models similarly utilized Metabolon's services to identify a serum metabolite that induced anxiety-like behavior in these mice. Interestingly, the levels of this metabolite were modulated by intestinal flora composition.⁹⁷ Using this approach, we will **identify novel bacterial metabolites, some of which may be LBP-derived, that are associated with modulation of aGvHD** and may play a role in either aggravating or attenuating inflammation.

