7.4 Specimen Collection, Processing and Shipping

7.4.1 Blood Specimens (Citrulline and Cytokines)

Sample Time Points:
	
 • First day of conditioning or anytime within 72 hours before the start of conditioning (prior to chemotherapy) • Day 0 (graft infusion) • Day 7 • Day 14 • Day 28 or discharge, whichever is first • Day 56 (citrulline only) 
Sample acquisition can occur within 72 hours before the first day of conditioning. Sampling can occur within 24 hours before or after designated collection times for D0, D7, D14, D28 without being considered a protocol deviation. D56 sampling can occur within 14 days without being considered a deviation.
								

Blood Collection Procedure:
	
Draw 6 mL of whole blood in a red top tube (supplied by site).
								

Specimen Processing:
	
 1. After collection, allow blood to coagulate at room temperature. 2. After coagulation (but within 1 hour after collection) centrifuge the blood samples at 4°C for 15 minutes at 3000 rpm. 3. Aliquot the serum (upper layer) into three 1.5 mL cryovials (0.5 mL of serum per aliquot). 4. Store frozen at -80°C (or -70°C) immediately after aliquoting. 								

Specimen Labeling:
	
Freezer-safe labels will be provided in specimen kits and must be used as specified in the Specimen Collection Manual. Each cryovial must be legibly labeled with: ACCL1633, COG Patient ID, Timepoint + Aliquot ID (to track individual vials), and Collection Date.
								

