Exploratory Aims 3 and 4: These aims will examine the effects of *LBP* introduction on the intestinal flora of pediatric alloHCT recipients. The association between *LBP* administration and bacterial genes and pathways, and bacterial metabolites will be evaluated with Pearson's correlation coefficient with possible transformation to approximate normality. In addition to confirming the significance, a 95% confidence interval will be estimated for each marker. The total length of the interval depends on the observed correlation; the length will be 0.53 if the correlation is 0.40 and 0.24 if the correlation is 0.8. In addition to correlation, bivariate scatterplots will be used to display the association between *LBP* administration and each marker. Finally, we will perform a descriptive analysis examining the association between GvHD outcomes and bacterial genes, pathways, and metabolites using Cox regression. Additional regression models will adjust for other known GvHD risk factors.

Exploratory Aim 5: This aim will examine the effects of *LBP* on pro-inflammatory cytokines in alloHCT recipients. We hypothesize that *LBP*-associated maintenance or restoration in the microbiota will attenuate serum levels of pro-inflammatory cytokines in the early post-transplant period. We will use the same analytic approach as described for exploratory Aim 2 above.

Exploratory Aim 6: This aim will examine the effects of LBP on the incidence (yes/no) of *Clostridium difficile*-associated diarrhea in alternative donor HCT patients. Patients who have at least one incidence (positive) of *C. diff* during any reporting period is considered evaluable for this aim. We will compare proportion of *C. diff* during the study period between arms via the chi-square test.

Exploratory Aim 7: This aim will examine whether LBP administration reduces hospital days within the first 120 days post hematopoietic cell transplant. Total hospital days over the study period is calculated as the duration between the date of admission for conditional therapy and the date of discharge (or the study end date). Hospital days will be compared between arms by t-test (or Wilcoxon rank-sum test if assumptions for t-test are not met).

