Exploratory Aims 1 and 2: The sample size for the primary aim drives the overall accrual goal and thus the number of subjects available for the exploratory aims. These endpoints will be analyzed only at the end of the study, either at the end of the screening stage or confirmatory stage. Therefore, the power is estimated for the two situations separately based on sample size of 120 (60 per arm) or 454 (227 per arm) without any adjustment for power after the confirmatory stage. For Exploratory aim #1, a baseline rate of Grade II–IV aGvHD in the range of 30%–50%, the sample size after confirmatory stage is sufficient to detect a 15% reduction in aGvHD rate, while the sample size after screening stage is sufficient to detect a 20% reduction in aGvHD rate with LBP compared to placebo. Power estimation is based on 2-sample test of proportions at $\alpha=0.05$ (2-sided). For Exploratory aim #2 on serum citrulline levels, the sample size after confirmatory stage is sufficient to

detect an effect size of 0.4 standard deviation (SD), assuming we obtain samples from 80% or more of the subjects; on the other hand, the sample size after screening stage is sufficient to detect an effect size of 0.7 SD if we obtain samples from $\geq 80\%$ subjects. Power estimation is based on two-sample t-test at $\alpha=0.0125$ (2-sided), where α is based on the Bonferroni adjustment for the 4 parallel comparisons with an overall $\alpha=0.05$.

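### Three exploratory planning statements do not match the design: four citrulline contrasts for five post-baseline draws, interval lengths that 30 samples do not give, and 60 per arm called sufficient at 63–81% power

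*Combined protocol and SAP*

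**What the plan says.** **Citrulline (Exploratory Aim 2).** Section 9.3 compares between arms "The mean quantitative change in citrulline level from start of conditioning to each of the four later time points", with a Bonferroni correction for four analyses. Section 9.4 uses two-sided alpha 0.0125, which "is based on the Bonferroni adjustment for the 4 parallel comparisons". The sampling sections schedule a baseline draw and then Day 0, Day 7, Day 14, Day 28 or discharge, and Day 56. Section 7.4.1 lists the last as "Day 56 (citrulline only"), the note to the table in Section 7.1 says "Citrulline sample only", and Section 7.3.1 says "Serum citrulline will be evaluated from the initiation of therapy to Day 56".

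**Correlations (Exploratory Aims 3 and 4).** Section 9.3 plans a Pearson correlation with a 95% interval for each gene, pathway or metabolite marker, and states that "the length will be 0.53 if the correlation is 0.40 and 0.24 if the correlation is 0.8". It gives no sample size. Section 7.3.3.1 says "We will randomly select a subset of 30 samples from patients with similar overall 16S abundance", 15 with abundant LBP and 15 with undetectable LBP. For metabolites, Section 7.3.3.2 says "We will profile aliquots of the same stool samples selected for the whole shotgun metagenomic sequencing approach detailed above".

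**Grade II–IV aGvHD (Exploratory Aim 1).** Section 9.4 takes a baseline rate of 30–50% and a two-sided 0.05 test of two proportions. It describes 227 per arm as sufficient for a 15% reduction and 60 per arm as sufficient for a 20% reduction. No power level is named. The 60-per-arm comparison applies if the study ends after the screening stage.

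**The concern.** Day 56 blood is drawn for citrulline alone, so it cannot be presumed to lie outside the citrulline analysis, yet the contrast count leaves one draw out. Four is the right count for the cytokines, which stop at Day 28. If the four contrasts are not named, the choice of which draw goes untested can be made after the data are seen.

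The interval lengths look too short for 30 samples. If so, the plan promises more precision for the profiling subset than it will deliver.

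The screening-stage claim covers a wide baseline range with a fixed absolute difference. Binomial variance grows as the rates move towards 50%, so power must fall across that range. If the trial stops after screening, 60 per arm is the only Grade II–IV comparison there will be, and a null result could be read as better powered than it was.

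**Working it through.** **1. Citrulline contrasts**

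- Plan's alpha: 0.05/4 = 0.0125, which reproduces.
- Post-baseline draws in Sections 7.1 and 7.4.1: Day 0, 7, 14, 28/discharge and 56, which is five. Bonferroni for five is 0.05/5 = 0.01.
- Power from the two-sample t-test (noncentral t), with samples from 80% of patients as Section 9.4 assumes: 0.8 × 60 = 48 and 0.8 × 227 ≈ 181 per arm.

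| Effect, n per arm | alpha 0.0125 | alpha 0.01 |
|---|---|---|
| 0.7 SD, 48 | 80.9% | 78.6% |
| 0.4 SD, 181 | 90.2% | 88.7% |

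Testing all five draws at 0.0125 has a Bonferroni bound of 5 × 0.0125 = 0.0625. The change scores share a baseline and are therefore correlated, so the actual error is lower. Simulation with 400,000 draws per setting gave 0.041–0.046. It used baseline SD 7 and follow-up SDs either 4.9/5.3/5.3/3.7/3.7 or all 5.3. The Day 0, 7 and 21 values come from the citrulline data in Section 2.5.1; the Day 14, 28 and 56 values, and equal correlations of 0 to 0.7, are assumed. Error above 0.05 is therefore not claimed.

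**2. Interval lengths**

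The Fisher interval is tanh(atanh r ± 1.96/√(n − 3)), with atanh 0.40 = 0.4236 and atanh 0.8 = 1.0986.

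Reproducing the plan's figures: at n = 40 the half-width on the z scale is 1.96/√37 = 0.3222, giving lengths 0.532 and 0.239. Over n = 5 to 499, only n = 40 gives both 0.53 and 0.24 to two decimals.

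At n = 30 the half-width is 1.96/√27 = 0.3772:

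- r = 0.40: 0.05 to 0.66, length 0.618, and 0.618/0.53 = 1.17.
- r = 0.8: 0.62 to 0.90, length 0.283, and 0.283/0.24 = 1.18.

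A 90% interval at n = 30 gives 0.523 and 0.235. A Wald interval at n = 30 gives about 0.60–0.63 and 0.26–0.27. Neither matches both stated figures.

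**3. Grade II–IV aGvHD with 60 per arm**

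The 20% is read as percentage points. Unpooled power = Φ(Δ/SE − 1.96), with SE = √{[p₁(1 − p₁) + p₂(1 − p₂)]/60} and Δ = 0.20. Example at 50% against 30%: SE = √[(0.25 + 0.21)/60] = 0.0876, so Φ(2.284 − 1.960) = Φ(0.324) = 62.7%.

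| Baseline vs LBP | Unpooled | Pooled |
|---|---|---|
| 30% vs 10% | 80.7% | 78.9% |
| 40% vs 20% | 68.8% | 67.0% |
| 45% vs 25% | 65.1% | 63.5% |
| 50% vs 30% | 62.7% | 61.1% |

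The 45% row is the upper figure for Grade II–IV aGvHD in Section 2.1. Arcsine and exact calculations also fall to about 62% at 50%. Unpooled power drops below 80% once the baseline exceeds about 30.5%. The difference detectable with 80% power is about 20 points at baseline 30%, 22.5 at 40% and 24–24.5 at 50%. Read as a relative reduction, the 20% would have only 11–19% power.

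The other claims of sufficiency in Section 9.4 hold up better: 15 points at 227 per arm has 90.5–97.3% power, and the two citrulline claims have 90.2% and 80.9%.

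**The case against.** The best case on the other side is that none of this drives a decision. Section 9.4 says the primary aim sets the accrual goal, and all three items are exploratory. That stands, and it limits the weight of the point.

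On citrulline, Section 9.3 also promises a by-arm description at every time point and says mixed models using all time points will be considered, so no draw would go unreported. Moving to 0.01 costs only about 1.5–2.3 points of power. Both are true, but the formally tested family is still undefined.

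On the interval lengths, Section 9.3 gives no n, so 30 is inferred. The Fisher interval also assumes two continuous variables and independent observations, whereas LBP administration may be binary and Section 7.3.3.1 selects samples at two extremes of LBP abundance. A point-biserial interval at n = 30 has lengths 0.577 and 0.250, which narrows the gap to about 9% and 4%. The caution about the model is fair. However, the plan's two figures match Fisher at n = 40, so the same method at n = 30 is a like-for-like restatement, and the alternative is still longer than stated.

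On aGvHD power, no target is stated and the claim roughly meets 80% at baseline 30%. Section 9.3 says Aim 1 follows the primary aim's approach, which is one-sided; at one-sided 0.05 power would be 88%, 79% and 74% at baselines 30, 40 and 50%. But the sentence at issue specifies a two-sided test, so 63–81% is its power.

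**Conclusion.** The concern holds on all three items.

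- The citrulline contrast count (four) disagrees with the draw schedule (five), and the four are not identified. The harm is an open analytic choice, not demonstrated error inflation.
- The stated interval lengths do not hold for 30 samples. By the method that reproduces them they should be 0.62 and 0.28, or 17–18% longer. This rests on linking the statement to the 30 profiled samples, the only samples the plan describes for gene, pathway and metabolite data.
- Sixty per arm has 80.7% power for a 20-point reduction only at the bottom of the stated range and 62.7% at the top. This rests on reading the 20% as absolute. Calling it insufficient depends on a benchmark the plan does not give; against the 81–97% of the other three claims in Section 9.4, this one is the outlier.

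The primary analysis and the sample size are unaffected.

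**What to change.** 1. In Sections 9.3 and 9.4, name the four citrulline contrasts to be tested and make the fifth draw descriptive, or test all five at alpha 0.01 and quote the powers of 78.6% (0.7 SD) and 88.7% (0.4 SD). This must be settled before unblinding.
2. In Section 9.3, restate the interval lengths as 0.62 and 0.28 for n = 30, naming the Fisher method, or state the n behind 0.53 and 0.24.
3. In Section 9.4, replace the screening-stage claim of sufficiency with the powers by baseline, or state the difference detectable with 80% power: about 20 to 24.5 points across baselines of 30–50%. Say that reductions are in percentage points.

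Optionally, as an efficiency gain and not a correction, name baseline citrulline as a covariate in the models Section 9.3 already lists.

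The cost is wording in the statistical section. A few exploratory figures become less favourable. No new data are needed, and the sample size and primary analysis do not change.
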